**D. Description, Risks and Justification of Procedures and Data Collection Tools:**

**Aim 1:** Study personnel will administer measures four times: enrollment (baseline), 4 months, 6 months and 12 months (**Table 5**). The baseline and 6-month measures which are comprised of approximately 120 questions and are expected to last 45 minutes, will be obtained during an in-person visit, by mail and phone or by video teleconference. We will allow patients to complete 4 month and 12 month measures by mail or phone if they prefer. Veterans will be offered an incentive for completing each of the 4 study visits (\$10 at baseline, \$10 at 4 months, \$15 at 6 months, \$10 at 12 months). Patient reported survey data is necessary to achieve study aims as the primary outcome is quality of life which is patient perceived. Demographic data and information from medical record review is necessary to determine secondary outcomes. We have implemented the following protections:

Table 5. Study Visits and Assessments	Baseline	Month 4	Month 6	Month 12
Demographics/study form	X			
FACT-G (primary outcome)	X	X	X	X
PHQ-8, GAD-7	X	X	X	
KCCQ-12, CCQ, K-BILD	X	X	X	
QUAL-E, Symptom Assessment, GSDS	X		X	
Advance care planning communication, assess for advance directive documentation	X		X	
Medications	X		X	
Health care utilization, vital status, risk of hospitalization/death			X	X
Use of other medical services	X		X	

Satisfaction	X	X
--------------	---	---

Medical record data will be gathered for up to ten years after each participant concludes active study participation. The purpose of this is to determine the effect of the intervention on long-term health and health care use. This could include but is not limited to hospital discharge summaries, progress notes, operative notes, laboratory results, and diagnostic tests.

Protection against loss of confidentiality.

To protect against loss of confidentiality, all research materials will be inaccessible to anyone other than the investigators and research staff. All source documents will be identified by study identification (ID) number, and the key to that ID will be kept in a locked file cabinet in a locked office of the site PI, study coordinator, or research assistant. All personally identifiable information also will be kept separately from data forms and in a locked file cabinet. No results will be entered into our data collection system or reported in a personally identifiable manner. Any non-VA healthcare records will be faxed to a fax machine in a restricted access room.

We will use the Research Electronic Data Capture (REDCap) system for electronic entry of deidentified outcome data. All tracking system data will be password-protected with several levels of protection. The first will allow access to the operating system of the computer. The second will allow access to the basic menus of the integrated system; within certain menu options, such as database browsing, a third password will be required. All user interaction with the web-based system, from transmission of access passwords to sensitive patient data, is done via 128-bit encryption using the secure HTTPS protocol. REDCap is also HIPAA-compliant. Data will be downloaded from VINCI REDCap to the local VA Server for analysis. Data for intervention patients will be stored on VA secure research servers designated for storage of protected health and identifiable information.

Protection against loss of privacy.

The majority of the interactions with study subjects will occur over the phone. Study personnel will make these phone calls from a private office or cubicle. At the beginning of any phone calls, study personnel will ask subjects if it is an acceptable time to talk and if privacy can be assured. We will accommodate study subjects by calling on different dates or times. For the recruitment visit and initial study visit that takes place in the hospital or clinic setting, we will also attempt to enhance privacy as much as possible if study subjects do not have a private room. For example, we will use a family conference room on the hospital unit or clinic and close curtains or doors.

**Table 6. Intervention implementation (Aim 2a) objectives, data collection, and analytic frameworks**

Objective	Data Source	Sample Size	Analytic Framework
Assess intervention component implementation	Intervention database	150	Quantitative : descriptive statistics by site and illness of the variability in "dose" and content of the delivered intervention
Identify critical intervention components and processes and facilitators/barriers to intervention implementation	Brief patient interviews	100	Qualitative analysis of data using the following CFIR* Domains, Constructs , allowing for emergence of new codes/ideas
	Intervention close out summary	150	Intervention Characteristics Relative advantage, complexity, cost, design quality and packaging
	Focused group discussion with intervention team	1-2	Characteristics of Individuals Knowledge & beliefs about Intervention
	Survey of PCPs whose patients have received the intervention	150	Outer Setting Patients' Needs and Resources Inner Setting Implementation climate, relative priority, readiness for implementation

\*CFIR, Consolidated Framework for Implementation Research

### Staff Training, Supervision and Quality Assurance.

The intervention manual and protocol, procedures for medical or psychological emergencies, procedures for protection of human subjects, and HIPAA requirements will be reviewed in detail in a pre-study meeting. The importance of adherence to intervention protocol will be stressed. The social workers will be trained in the intervention and how to provide psychosocial care. This will include training to review the theory underlying the counseling, a review of the treatment manual and patient materials, and role-playing to show the appropriate application of the counseling. Study training will also include training for the study nurse who is conducting the palliative symptom management algorithms and coordinating the collaborative care team. This training will review the symptom management algorithms and procedures for unanticipated events (e.g., a subject complains of chest pain while on the phone). Day-to-day supervision and study fidelity and quality assurance will be maintained by the PIs.

### Data management/Data quality

To ensure data integrity, the study protocol manual will include a section on data collection with descriptions of each data element or measure and instructions for its accurate collection or acceptable source. Several strategies will be used to avoid missing data and dropout, such as follow-up phone calls and letters. The study will use VA research servers for building and managing online databases.

### Monitoring plan

Monitoring will focus on recruitment, baseline comparability of treatment groups, protocol adherence, completeness of data, accrual of primary endpoint data, safety, and follow-up rates. This monitoring will provide the basis for reporting to a Data Safety and Monitoring Board and quarterly review by the study investigators.

In the event we discover a serious medical or psychological problem in the usual care group, a referral will be made to appropriate medical and/or psychological professionals. Participants will be encouraged to access resources provided by their personal health team as well as community resources.

### Study Procedures for Positive Depression Screening:

The outcome measures administered to all subjects include a screen for depression (a score of greater than 10 on the PHQ-8). Because the intervention focuses on depression, these issues will be addressed in intervention subjects as part of the intervention. Subjects in the *usual care* group who score above the screening cutoff for moderate depression will be advised of this and given resources for depression care, including advice to discuss these results with a health care professional. In addition, the results will be forwarded to their health care professional.

**Aim 2a:** To understand why particular intervention components and processes were most critical from the perspectives of patients, intervention team members, and PCPs, we used the Consolidated Framework for Implementation Research (CFIR) to guide data collection (**Table 6**). CFIR, which is well-established in VA, was chosen as it provides a useful framework for considering contextual facilitators and barriers to intervention implementation. Specific domains and constructs from CFIR were chosen to reflect the areas that were important to patients, intervention team members, and providers in the CASA pilot study. The following data sources will be used for Aim 2a:

*Intervention database:* The following data will be collected: (1) team meeting duration, number of patients discussed and time spent per patient, medical orders (e.g., tests, medications) written and completed; (2) nurse and social worker visit duration, number, and content (using a brief checklist) for each patient.

*Brief patient interviews:* After the outcome measurement at 6 months, we will conduct brief in-person or telephone interviews with Veterans randomized to the intervention arm. Interviews will be conducted to elicit patient views about different parts of the intervention (e.g., nurse vs. social worker); how to improve the content and value of the intervention; communication and coordination; and to what extent they continue to sustain their use of the intervention after the study. We will continue to interview as staff time permits or until no new information emerges from continuing interviews, a principle known in qualitative research as “saturation.” We will interview a subset of patients completing the intervention every 6 months in order to account for potential

differences over time (e.g., intervention provider experience). We will seek variability in the sample we interview (e.g., by sampling from both study sites and sampling patients who benefit the most and least from the intervention based on changes in the FACT-G score at 6 months or participant ratings of helpfulness). Interviews will be audio-recorded using a secure recording mechanism or an audio recording device. Detailed notes will be taken during the interviews. Interviews will be transcribed verbatim by VA contracted transcription service or a member of the study team. All interviews will be de-identified and all PHI/PII will be removed before transcribed.

***Intervention Close Out Summary:*** This 1-page summary form will capture information from intervention providers on what worked well and not so well with components of the intervention, what was missing, and whether the patient engaged in and followed up with behavioral changes.

***Focused Group Discussion with Intervention Team:*** The goal of this discussion is to elicit intervention team views about what worked well; what parts of the intervention might be streamlined, dropped or enhanced; and their views about patient, family caregiver, and PCP receptivity and responsiveness. A qualitative researcher will lead these focused group discussions which will be recorded and transcribed

***Surveys of PCPs:*** Using a combination of rating scales and a few open-ended questions, the goal of these surveys is to efficiently identify strong positive or negative opinions about the usefulness of different intervention components, integration of the intervention into work flow, and the perceived impact of the intervention on quality of care. We will also ask for their insights into ways to sustain and spread the intervention to other urban and rural VA sites. The questions were selected to explore specific CFIR constructs of importance. Providers will complete the survey via phone, in-person, or via e-mail.

**Aim 2b:** In addition to the above data collected for Aim 2a that are associated with the intervention content and processes, we will also use methods and instruments described in Ritzwoller et al 2009 to evaluate the resources and costs to implement and maintain the intervention. These resources and costs will be measured from the perspective of each VA health care system site. The rationale for this perspective is that each health care system (ECHCS and PSVAHCS) has budgetary and administrative authority over implementing programs such as the proposed intervention. Resources associated with the program will be classified as labor (e.g., nurse intervention time) or non-labor (e.g., supplies, printing of patient materials) and recorded using Excel spreadsheets. Costs for research (e.g., grant administration, IRB approvals, informed consent, analysis) will not be included.

## **E. Potential Scientific Problems:**

1. *Recruitment problems.* The recruitment goals are modest, reasonable for each site, and were planned based on the investigators experience with similar prior trials. If necessary, resources can be diverted to increase efforts at one of the recruitment sites. We can also add recruitment of inpatients at the sites' VAMCs using the same enrollment criteria and conduct a sensitivity analysis to determine if outcomes are different for those recruited in this setting.

2. *Limits of administrative data for the diagnosis of CHF, ILD, or COPD.* While the administrative codes used to identify patients with CHF or COPD have been validated, they are not perfect and some Veterans will be enrolled who do not have these illnesses. However, all enrolled Veterans will be appropriate for the intervention because they will (1) be at high risk of hospitalization and death, (2) have poor quality of life, and (3) be symptomatic. The team will recommend appropriate evaluation and management for all Veterans. For example, this may include a spirometry test to evaluate for COPD if it was not previously done.

3. *Palliative care elements such as spiritual care are not explicitly mentioned.* The palliative care specialist is on the team to bring all aspects of palliative care to patient care. In addition, social workers have basic spiritual assessment and management skills. If spiritual distress is identified, for example, the team can enlist assistance from a chaplain or the Veteran's religious community.

4. *If the intervention is not successful in showing improvements in any of the outcome measures*, this will be an important, if undesired result, but study will still contribute to the evidence base regarding models of palliative care delivery. The process monitoring will inform future interventions.
5. *This is a personnel intensive intervention*. Compared to a traditional palliative care consultation in which a specialist palliative care team (physician, nurse, social worker, chaplain) all provide direct patient care, the intervention was designed to use much less personnel time. Most of the intervention is delivered by phone. We will track the personnel time and other costs associated with the intervention (Aim 2b).

## **F. Data Analysis Plan:**

### **Aim 1 Data Analysis**

*Descriptive Statistics and Basic Comparisons.* All analysis variables, including predictors, covariates, and outcomes, will be examined carefully prior to any formal statistical analysis. Standard graphical methods, including histograms and boxplots, will be used to examine overall distributions and identify potential outliers, which will be confirmed prior to inclusion in analysis. Internal consistency of multi-item scales will be examined using Cronbach's alpha, and whenever possible, items and scales will be compared to existing findings on their psychometric properties to ensure appropriate performance. Data transformations will be considered, such as log transformations for highly skewed data, to meet model assumptions. Each measure will be summarized using standard descriptive statistics, including means and standard deviations, medians, and ranges for continuous measures and proportions for categorical measures. Baseline characteristics will be compared between groups using appropriate tests, such as Chi-square and t-tests.

*Primary/Secondary Analyses.* Data from all participants will be included regardless of level of participation using an intent-to-treat approach. The primary outcome measure, FACT-G, will be analyzed as a continuous variable, while the secondary outcomes will be either continuous (disease-specific health status, depression, symptom burden, emergency department visits, hospitalizations) or binary (advance care planning communication and documentation; mortality). Due to the short follow-up period, time-to-event analyses will not be used. Analyses of the repeated measures, including primary and secondary endpoints, will be performed with SAS 9.4 using maximum likelihood estimation (MLE) for incomplete data using linear mixed models for continuous outcomes and generalized linear mixed models with a logit link for binary endpoints. This approach has several advantages: 1) all available data on eligible subjects can be included in the analysis even when there are missing data at follow-up, 2) MLE estimates the correlation between related measures and adjusts test statistics appropriately, 3) time-varying covariates can be incorporated into the model, if desired, and 4) the assumptions about missing data are relaxed from missing completely at random to missing at random. The primary analyses will not consider the pre-randomization variables, but the effect of these variables on outcomes will be investigated as secondary analyses. We will add a random intercept for PCP to the analytic models to account for clustering of outcomes by practice patterns.

The primary outcome will be the difference in FACT-G score at 6 months. Because of the anticipated high correlation of baseline FACT-G with follow-up FACT-G ( $r>0.5$ ), we will include the baseline FACT-G as a precision variable in the mixed model. To describe the treatment by disease interaction, we will estimate the treatment effect and its confidence interval within each of the disease groups (CHF, ILD, COPD) using disease-specific health status measures (KCCQ, K-BILD, CCQ) at the 6 month endpoint. In exploratory analyses, we will estimate treatment effect within illness subgroups (CHF, ILD, and COPD) on the primary outcome, and within subgroups of illness, including CHF (preserved vs. reduced ejection fraction) and COPD (defined by spirometry and imaging). Missing data will be reviewed to identify potential patterns and examined to assess how these patterns impact our results. Specifically, we will examine plots of group means over time stratified by the time of the last completed observation to determine if biases are evident due to missing data. When data are missing at random, unbiased results can still be obtained from the likelihood method used in the analysis. To account for the possibility of data missing not at random, sensitivity analyses will be performed using pattern mixture models and results will be presented to assess the impact of missing data on the reported conclusions. Among those who were hospitalized or died, we will examine for differences in

intensive care utilization and patterns of care at the end of life. We will also examine for intervention effect on longer term health care utilization (e.g., hospitalization, intensive care utilization).

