#### Sample Size

The sample size was planned to detect a clinically significant change on the primary outcome, quality of life. We plan to enroll 400 Veterans and anticipate 5% will die and 15-20% will have missing outcome data because they did not complete surveys or dropped out. Thus approximately 115 Veterans per arm will complete the study. With this sample size, we will have 85% power to detect a moderate effect size of 0.4 (two-sided test, alpha=0.05). The minimal clinically important difference on the FACT-G is 4-6 points, and with a standard deviation of 15, a Cohen's d effect size of 0.4 will be on the high end of clinical significance. We believe this is appropriate as this is a personnel-intensive intervention. **Table 3** illustrates a range of sample sizes per study arm with different power and effect size assumptions.

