**Advancing Symptom Alleviation With Palliative Treatment (ADAPT)**  
**NCT02713347**  
**IIR 14-346**

**November 15, 2021**

**ADAPT Data Analysis Plan:**

Data from all participants will be included regardless of level of participation using an intent-to-treat approach. The primary outcome measure, FACT-G, will be analyzed as a continuous variable, while the secondary outcomes will be either continuous (disease-specific health status, depression, symptom burden, emergency department visits, hospitalizations) or binary (advance care planning communication and documentation; mortality).. Analysis models will adjust for the disease stratification variable used in randomization. Analyses of the repeated measures, including primary and secondary endpoints, will be performed with SAS 9.4 using maximum likelihood estimation (MLE) for incomplete data using linear mixed models for continuous outcomes and generalized linear mixed models with a logit link for binary endpoints. This approach has several advantages: 1) all available data on eligible subjects can be included in the analysis even when there are missing data at follow-up, 2) MLE estimates the correlation between related measures and adjusts test statistics appropriately, 3) time-varying covariates can be incorporated into the model, if desired, and 4) the assumptions about missing data are relaxed from missing completely at random to missing at random (Little RJ. Methods for handling missing values in clinical trials. *J Rheumatol* 1999;26(8):1654-1656). The primary analyses will not consider the pre-randomization variables, but the effect of these variables on outcomes will be investigated as secondary analyses.

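### The plan does not specify that each continuous secondary scale's own baseline enters its model, so those effects may be estimated less precisely than the data allow

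*Protocol*

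**What the plan says.** Protocol Table 5 (section D) schedules PHQ-8, GAD-7, KCCQ-12, CCQ and K-BILD at baseline, month 4 and month 6. The row "QUAL-E, Symptom Assessment, GSDS" is marked at baseline and month 6 only.

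The protocol's Aim 1 Data Analysis section expects baseline and follow-up FACT-G to correlate above 0.5 and therefore states "we will include the baseline FACT-G as a precision variable in the mixed model". No secondary scale gets a corresponding statement. The within-disease treatment effects are to be estimated "using disease-specific health status measures (KCCQ, K-BILD, CCQ) at the 6 month endpoint", with no mention of baseline.

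The SAP puts all continuous outcomes into linear mixed models for repeated measures and adjusts them for the disease stratum. It defines a change-from-baseline effect for FACT-G only. Like the protocol, it says: "The primary analyses will not consider the pre-randomization variables, but the effect of these variables on outcomes will be investigated as secondary analyses". Neither document states whether a secondary scale's baseline is a covariate, a response with free means, or a response with means held equal across arms.

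**The concern.** The protocol's reason for adjusting FACT-G is that a score predicts its own later value. That reason applies to any scale given to the same patient twice, and the data are already scheduled. Yet the plan leaves open at least three analyses of each secondary scale, and two of them discard precision.

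Three of the seven outcomes listed in Aim 1(b) are affected: depression, symptom burden and disease-specific health status. GAD-7 and QUAL-E are related scales outside that list. The disease-specific measures are given only to patients with the relevant disease, so those estimates come from subsets of the sample. The protocol's Study population section itself expects few patients with ILD.

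In a single dataset the 6-month, change and adjusted estimates will differ when baselines differ by chance. Leaving the form open therefore also leaves open which number is reported.

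**Working it through.** **Inputs from the plan.** Protocol, Sample Size: "two-sided test, alpha=0.05"; "Thus approximately 115 Veterans per arm will complete the study"; "we will have 85% power to detect a moderate effect size of 0.4"; "with a standard deviation of 15, a Cohen's d effect size of 0.4". The baseline-to-follow-up correlation r is given for FACT-G only, as above 0.5.

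**Assumptions.** The documents give no r for any secondary scale, no disease-group sizes, and no effect size or power target for any secondary outcome. I take r from 0.4 to 0.7, and illustrative groups of 60, 40 and 20 per arm.

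**Plan's own figure.** A two-sample t-test with 115 per arm, d = 0.4 and two-sided alpha 0.05 has power 85.6%, which agrees with the stated 85%. All nine cells of Table 3 also reproduce. The calculation takes no credit for baseline.

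**Variance of the 6-month treatment contrast.** This is relative to a 6-month-only comparison, with complete data and equal SD at both times:

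- 6-month only: 1
- change, or baseline as a response with unconstrained means: 2(1 − r)
- own baseline as covariate, or baseline means constrained equal: 1 − r²

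The ratio of adjusted to change is (1 − r²)/[2(1 − r)] = (1 + r)/2. Since 1 − r² ≤ 1 and (1 + r)/2 ≤ 1, adjustment is never less precise than either alternative, apart from one degree of freedom.

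| r | 6-month | Change | Adjusted | Cut vs 6-month | Cut vs change |
|---|---|---|---|---|---|
| 0.4 | 1 | 1.20 | 0.84 | 16% | 30% |
| 0.5 | 1 | 1.00 | 0.75 | 25% | 25% |
| 0.6 | 1 | 0.80 | 0.64 | 36% | 20% |
| 0.7 | 1 | 0.60 | 0.51 | 49% | 15% |

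At r = 0.5 the standard error is multiplied by √0.75 = 0.87, so the confidence interval is 13% narrower. Below r = 0.5 a change contrast is noisier than ignoring baseline.

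Simulation with 115 per arm gave relative variances for the 6-month, change and adjusted estimates of 1.05, 1.01 and 0.79 at r = 0.5, and 1.05, 0.60 and 0.52 at r = 0.7. These agree with the formulas within simulation error.

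**Power.** Two-sample t-test with d divided by the square root of the relative variance:

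| n per arm | d | r | 6-month | Change | Adjusted |
|---|---|---|---|---|---|
| 115 | 0.4 | 0.4 | 85.6% | 78.7% | 90.9% |
| 115 | 0.4 | 0.5 | 85.6% | 85.6% | 93.7% |
| 115 | 0.4 | 0.7 | 85.6% | 97.4% | 98.8% |
| 160 | 0.4 | 0.5 | 94.6% | 94.6% | 98.5% |
| 160 | 0.3 | 0.5 | 76.3% | 76.3% | 87.1% |
| 60 | 0.4 | 0.5 | 58.4% | 58.4% | 70.9% |

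The 160 rows are included because the protocol's own attrition leaves more than 115 per arm: 400 × (1 − 0.05 − 0.15)/2 = 160, or 400 × (1 − 0.05 − 0.20)/2 = 150.

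**Disease groups.** The 95% half-width in SD units is 1.96 × √(2v/n), where v is the relative variance. At r = 0.5, v falls from 1 to 0.75:

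| n per arm | Unadjusted | Adjusted | Reduction |
|---|---|---|---|
| 60 | 0.36 | 0.31 | 0.05 |
| 40 | 0.44 | 0.38 | 0.06 |
| 20 | 0.62 | 0.54 | 0.08 |

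The proportional reduction is 13% in every row. Only the absolute reduction grows as the group shrinks.

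**The case against.** A reader might infer that the secondary models ignore baseline altogether. The documents do not establish that. They call these analyses repeated-measures mixed models, and for GSDS, QUAL-E and the symptom scales, measured only at baseline and month 6, such a model is possible only with baseline among the responses. If the baseline means are also held equal across arms, the model already captures almost all the gain. What stands against the plan is that neither document states that constraint, and a conventional group-by-time model does not impose it.

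A reader might take "using disease-specific health status measures (KCCQ, K-BILD, CCQ) at the 6 month endpoint" as a follow-up-only analysis. It names a time point. The protocol defines the FACT-G outcome at 6 months in the same way and then adjusts it for baseline.

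A reader might take the sentence on pre-randomization variables as a ban on these baselines. Its wording limits the primary analyses and allows such variables in secondary ones, and the protocol itself admits baseline FACT-G and names the TICS as a covariate. That allowance does not close the gap, because it concerns the variables' effect on outcomes and does not say which treatment estimate is reported.

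The size is also open to challenge. It rests on an assumed r, assumed group sizes and an effect size borrowed from FACT-G. At 160 per arm and d = 0.4 the gain at r = 0.5 is about 4 points. Against a change analysis at r = 0.7 and 115 per arm it is 1.4 points (97.4% to 98.8%). These objections limit the claim but do not remove the gap.

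**Conclusion.** The point holds as a gap in specification with a cost in precision. Own-baseline use is unspecified for every continuous secondary scale, although each baseline is collected and the protocol makes the precision argument for FACT-G.

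With r assumed to be 0.4 to 0.7, adjustment cuts the variance by 16 to 49% against a 6-month comparison and by 15 to 30% against change. Against a model with constrained baseline means the further gain is about zero. The proportional gain is the same in every disease group, so the disease groups do not lose relatively more. They gain more only in absolute interval width, and only to the extent that they are small.

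Bias should not be inferred. Under randomization each candidate estimator is unbiased with complete data, and the standard error of a 6-month comparison already reflects chance baseline imbalance. The point also does not cover most of Aim 1(b). It concerns three of the seven outcomes there, plus related scales.

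**What to change.** Add to the SAP, after the sentence on the disease stratum: *The model for each continuous secondary scale (PHQ-8, GAD-7, GSDS, QUAL-E domains, symptom scales, KCCQ-12, CCQ, K-BILD) will include that scale's own baseline value as a covariate, with post-baseline visits as responses. The treatment effect is the adjusted difference at 6 months. The same model will be used for the within-disease estimates.*

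An equivalent choice is a longitudinal model with baseline as a response and baseline means constrained equal across arms. It also keeps patients who have a baseline but no follow-up survey. Name one of the two.

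Clarify as well that the sentence on pre-randomization variables does not exclude these baseline scores.

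The cost is one or two sentences and one degree of freedom per model. No new data, visits or staff are needed.
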